9.1.2. Post-Database Lock

Upon study completion and locking of the database, participants will return for a final visit to receive their final clinical laboratory tests and unblinding assignment. Participants who received active investigational product will be counseled that these remain experimental candidate vaccines that have no proven ability to protect against subsequent HIV infection, so continued appropriate precautions for HIV behavioral prevention must be exercised. In the event that an individual participant has undergone vaccine-induced seroreactivity, they will be informed that they may face discrimination if undergoing a HIV testing outside the clinic facility, as disclosed in the informed consent. These participants will be offered the opportunity to return to the clinic for routine monitoring of seroreactive status every 6 months as a clinical service even after study closure until it disappears.

9.1.3. Mucosal Secretion Collection

Mucosal secretion collection (cervico-vaginal, semen, rectal secretions, vaginal swab, endocervical cytobrush/swab, penile swab and rectal swab) will be performed at Visits 1, 4, 5, and 6 on participants who provide separate informed consent for these procedures.

Consenting women will have a pelvic examination done by an experienced doctor, who will inspect the tissue of the vagina and cervix and will collect endocervical cells using an endocervical cytobrush/swab as well as collecting a vaginal swab to assess the microbiome/proteome. Participants will also complete the FGT questionnaire. After the examination, the participant will be instructed on how to use a menstrual disc device to collect cervical and vaginal secretions by either self-insertion the night before the visit or the morning of the visit, or with assistance by trained clinic staff during the visit. Participants who choose self-insertion will be given a menstrual disc at a prior visit and instructions ([Appendix T](#)) on how to insert the menstrual disc on the night before or the morning of the collection visit. The menstrual disc will remain in place for 4 to 12 hours. Female participants will be asked to avoid receptive vaginal intercourse or insertion of objects intravaginally (tampons, douching, etc.) for the 3 days prior to specimen collection. Pregnant women and those with a history of toxic shock syndrome will be excluded. Collection will not take place if the woman is menstruating or has symptoms of active inflammation or infection of the vagina or cervix. For participants who choose to self-insert the menstrual disc, study staff will call the participant the day before their study visit to remind them about inserting the menstrual disc and to ask about pregnancy, menstruation, and any abnormalities that may preclude them from using the menstrual disc. Participants will be advised to not self-insert the menstrual disc as necessary. For menstruating females, mucosal collection window can be extended to -3/+14 days. The date of last menstrual period will be recorded at each collection visit and blood samples for hormone levels will be evaluated. If,

during the course of the study, a woman becomes pregnant, she will be excluded from further genital secretion collections.

Consenting men will have a brief visual examination at the screening visit which will be completed by an experienced doctor who will inspect the participant's penis for signs or symptoms of urethral inflammation. The participant will be given instructions ([Appendix U](#)) on how to self-collect the swabs and will be asked about any signs or symptoms of urethral inflammation prior to the collection of penile swabs and/or a semen sample at follow-up visits. Both penile swabs and semen collections will be deferred if there are signs or symptoms of urethral inflammation. Penile swab will be collected by full circumference of the penis at the coronal sulcus, the junction between the glans and the shaft of the penis. This procedure can be completed by the participant after receiving instruction from study staff or if the participant prefers, the study staff can complete the collection. For the semen collection, the participant will be asked to ejaculate into a sterile container. A private room in clinic will be provided for both procedures. Male participants providing semen will be asked to avoid ejaculation for the 3 days prior to specimen collection.

Both male and female participants may elect to provide rectal secretions and rectal swabs for microbiome/proteome assessment. Participants providing rectal secretions will be asked to avoid receptive anal intercourse or insertion of objects into the anus (enema, etc.) for the 3 days before specimen collection. The anal rectal sponge will be inserted and removed by trained medical staff and will be placed in the rectum for a maximum of 5 minutes. Examination and specimen collections take up to 30 minutes to complete. Rectal sponge and swab collections will be deferred if there are signs or symptoms of perianal inflammation. Gastrointestinal and dietary questionnaires will be administered to all participants who choose to collect rectal secretion/swab collection.

9.1.4. Sigmoid Biopsy

Sigmoid biopsies will be performed only at Visit 4 on participants who provide separate informed consent for the procedure. The procedure will be performed by trained personnel at the King Chulalongkorn Memorial Hospital in Bangkok, Thailand.

Prior to undergoing a sigmoid biopsy, participants will be tested for COVID-19 (if required by institutional procedures) and a pregnancy test will be performed on female participants. All participants tested for COVID-19 must have a negative test result to proceed with the biopsy. Female participants must also have a negative pregnancy test to proceed. Participants who test positive for COVID-19 will be referred for care and treatment if required by institutional procedures.

Gastrointestinal and dietary questionnaires will be administered to all participants who choose to undergo a sigmoid biopsy prior to the procedure.

Using a GI endoscope, a gastroenterologist will collect about 16 to 30 tissue samples from the participant's gut. This procedure carries the possibility of pain, so prior to and during the sigmoid biopsy a licensed physician will offer participant intravenous sedative and pain medications. Medication will be provided to the participant free of charge by the study team. The use of aspirin and non-steroid anti-inflammatory drugs by participants will be prohibited 7 days before and 1 day after the procedure. Participants who undergo sigmoid biopsies will also be

asked to avoid receptive anal intercourse 3 days before and 7 days after the biopsy. The sigmoid biopsy procedure will take up to 1.5 hours to complete and participants will be observed for about 3 hours post-procedure.

9.1.5. Leukapheresis

Leukapheresis will be performed only at Visit 4 on participants who provide separate informed consent for the procedure. The procedure will be performed by trained personnel at the King Chulalongkorn Memorial Hospital, the Thai Red Cross AIDS Research Centre, or the Institute of HIV Research and Innovation (IHRI) Foundation.

For the leukapheresis procedure, participants will be connected to a cell separator machine via IV, which will separate white blood cells for laboratory testing while returning red blood cells either through the same needle or through a second needle placed in the opposite arm. When the procedure is completed, the maximum total red blood cell loss is about 10 mL (less than one tablespoon). Participants who undergo the leukapheresis procedure will not have blood drawn for immunogenicity assays at Visit 4. In addition to the white blood cells that are collected, approximately 150 mL of plasma will be removed at the end of each leukapheresis procedure for storage. Participants who undergo leukapheresis will have blood collected by phlebotomy in accordance with the SOE ([Table 3](#)), however they be exempted from the immunogenicity blood draw scheduled at the same visit. An additional 8.5ml of blood will be collected from these participants for PBMC and plasma storage in order to have comparator cells from each visit. Leukapheresis will be performed on participants whose platelet counts or hemoglobin counts meet the protocol inclusion criteria.

The entire procedure will take up to 2-3 hours, during which time the participant will be under constant observation by trained leukapheresis staff. If tingling in the face, lips or hands is experienced, study staff may offer calcium carbonate tablets to correct the calcium loss. Leukapheresis can occasionally cause nausea and may temporarily lower platelet count. More rarely, vomiting, fainting, seizures, dizziness, muscle cramps, itching, flushing, or burning sensation, rash, swelling of hands and feet, headache, nasal congestion, sneezing, wheezing, or chest tightness can occur. After the procedure is complete, participants will be observed for 30 minutes.

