⁶ The blood volumes drawn are in accordance with the Thai National Blood Bank policy: donation every 3 months but no more than 4 times a year; the amount of blood for each donation is according to weight that applies to both male and female: >50 Kg, 450 mL; ≤50 Kg, 350 mL. For participants who weigh below 50 Kg, blood for “Additional Immunogenicity Testing” will not be collected at Visits 1, 3 and 4 and only 25 mL of blood will be collected for “B-Cell Analysis” at Visits 1, 3, and 4.

⁷ Participants who consent for optional mucosal collections (semen, penile, rectal, and cervico-vaginal secretions, and cytobrush) and sigmoid biopsies will undergo additional testing for gonorrhea/chlamydia genital infections. Female participants who consent for optional mucosal collections will also undergo a pelvic examination that includes a Pap smear (if not done in 2 years prior to the mucosal collection) and visual inspection to evaluate for abnormalities. Female participants who choose to self-insert the menstrual disc collection device will be given instructions for self-insertion ([Appendix T](#)). Male participants who consent for optional mucosal collections will undergo a brief visual examination at the screening visit to assess the presence of urethral inflammation and will be given instructions for self-collection ([Appendix U](#)). Abnormalities that affect the participant’s safety or welfare or those that would increase the risk to a participant will preclude their participation in optional procedures.

⁸ Vitals to be collected both pre- and at about 30 minutes post-vaccination at Day 0.

⁹ Due to the time required to receive results of HIV testing, post-test counseling will occur at the next study visit after the results are available. HIV testing will be completed as described in Section [11.1.4.4](#) and management of positive results will be as described in Section [9.5](#).

¹⁰ Up to 10mL of blood will be drawn for safety tests within 2 days before the biopsy procedures for safety purposes. For the leukapheresis procedure, up to 10mL of blood will be drawn for safety tests within 2 days before and after the procedure for a total of 20mL of blood collected across both blood draws.

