Participants agreeing to optional mucosal collections (semen, penile, rectal, cervico-vaginal secretions, and cytobrush) and sigmoid biopsies will undergo additional testing to evaluate for sexually transmitted infections. This includes testing for gonorrhea/chlamydia by urine NAAT and by rectal swabs for individuals practicing receptive anal intercourse in the 6 months prior to testing for those undergoing rectal secretion collection or sigmoid biopsy. Female participants will undergo a pelvic examination that includes Pap smear testing with visual inspection to evaluate for further abnormalities. Individuals with abnormalities noted on examination and laboratory testing not explained by these conditions may undergo additional testing (e.g., wet prep for *Trichomonas vaginalis* in female participants) or be referred for further care and treatment. Abnormalities that affect the participant's safety or welfare or those that would increase the risk to a participant will preclude their participation in optional procedures.

The PI or designee will make the final decision regarding eligibility. Clinical data and specimens collected during screening from participants subsequently found to be ineligible for participation in the study will become part of the study records and specimens will be evaluated in accordance with protocol procedures. Only eligible participants will be given the investigational product at the enrollment visit.

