8.4. Inclusion Criteria

Participants must meet all of the following criteria to be included in the study:

1. Healthy, HIV-uninfected male and female participants
2. Prior RV306 recipients who were randomized to receive active vaccine with late boosting at month 12, 15, or 18 and who completed all vaccinations
3. Have a Thai identity card
4. Must be at low risk for HIV infection per investigator assessment
5. Must be able to understand and complete the informed consent process
6. Must be capable of reading Thai
7. Must successfully complete a Test of Understanding prior to enrollment
8. Must be in good general health without clinically significant medical history
9. HIV-uninfected per diagnostic algorithm within 45 days of enrollment
10. Laboratory screening analysis:
 - a. Hemoglobin: Women ≥ 11.0 g/dL, Men ≥ 11.5 g/dL
 - b. White cell count: 4,000 to 11,000 cells/mm³
 - c. Platelets: 150,000 to 450,000/mm³
 - d. ALT and AST ≤ 1.25 institutional upper limit of reference range
 - e. Creatinine: ≤ 1.25 institutional upper limit of reference range
 - f. Urinalysis: blood and protein no greater than 1+ and negative glucose

Note: Each laboratory screening test that is out of acceptable range can be repeated during the screening window to confirm the result. A second screening visit may be conducted outside of the initial screening visit window for individuals who meet certain criteria (see Section 8.3.1) only if study enrollment is ongoing.

11. Female-Specific Criteria:
 - a. Not currently pregnant or breastfeeding and not planning to become pregnant during the first 3 months after study vaccine/placebo injections
 - b. Negative pregnancy test for women at screening, prior to vaccination (same day), and prior to any of the invasive procedures
 - c. Be using an adequate birth control method for 45 days prior to receipt of vaccine/placebo and for at least 3 months after receipt of the vaccine/placebo.

Adequate birth control is defined as follows: Contraceptive medications delivered orally, intramuscularly, vaginally, or implanted underneath the skin, surgical methods (hysterectomy or bilateral tubal ligation), condoms, diaphragms, intrauterine device, or abstinence.

12. Male-Specific Criteria

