8.5. Exclusion Criteria

Participants meeting any of the following criteria will be excluded from the study:

1. Asplenia: any condition resulting in the absence of a functional spleen
2. Bleeding disorder diagnosed by a medical doctor (e.g., factor deficiency, coagulopathy, or platelet disorder requiring special precautions)
3. History of allergic reaction, anaphylaxis, or other serious adverse reaction to vaccines or components of the vaccines
4. Volunteer has received any of the following substances:
 - a. Chronic use of therapies that may modify immune response, such as IV immune globulin and systemic corticosteroids (in doses of ≥ 20 mg/day prednisone equivalent for periods exceeding 10 days)
Note: The following exceptions are permitted and will not exclude study participation: use of corticosteroid nasal spray for rhinitis, topical corticosteroids for an acute uncomplicated dermatitis; or a short course (duration of 10 days or less, or a single injection) of corticosteroid for a non-chronic condition (based on investigator clinical judgment) at least 14 days prior to enrollment in this study.
 - b. Blood products within 120 days prior to HIV screening
 - c. Immunoglobulins within 30 days prior to HIV screening
 - d. Any licensed vaccine within 14 days prior to study vaccine administration in the present study
 - e. Receipt of any investigational HIV vaccine other than RV306 products
 - f. Investigational research agents or vaccine within 30 days prior to enrollment in the present study
 - g. Receipt of a Coronavirus disease 2019 (COVID-19) vaccine that has been given Emergency Use Authorization (or those that become licensed) by the Thai FDA within 14 days prior to study vaccine administration in the present study
Note: Volunteers receiving a COVID-19 vaccine that requires 2 doses will not be enrolled until 14 days after the second dose has been administered
 - h. Anti-tuberculosis prophylaxis or therapy during the past 90 days prior to enrollment
- Note: Participants determined to be ineligible at screening due to receipt of the above listed substances may be re-screened once the applicable window of receipt has expired.*
5. Active sexually transmitted infection confirmed by clinical exam and diagnostic test

6. Any medical, psychiatric, social condition, occupational reason, or other responsibility that, in the judgment of the investigator, is a contradiction to protocol compliance or impairs a volunteer's ability to give informed consent

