8.6.1. Investigator Withdrawal of Participants

The PI may withdraw a participant without their consent for the following reasons:

- Failure to comply with study procedures or requirements
- A participant's health or safety may be compromised by further participation
- The PI assesses that it's not in the best interest of the participant to continue participation in the study

If a participant is withdrawn by an investigator, the reason should clearly be stated in the source documents and on the status change CRF.

When a participant withdraws due to an AE or is withdrawn by the PI due to an AE, the sponsor's safety office, the USAMRDC ORA PSSO, must be notified within 5 business days ([contact]). Investigators must follow specific policies regarding the timely reporting of AEs and SAEs to the IRBs (Section 11.8.1.2).

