9. STUDY PROCEDURES

9.1. Vaccination and Follow-up Visits

9.1.1. Day 0 Through Day 336

Day 0 is defined as the day of protocol enrollment and vaccine/placebo injections. At the enrollment visit, screening results will be reviewed and general eligibility will be assessed. All screening results, including results from any repeat testing, must be received prior to enrollment. Repeat testing will not affect the post-screening enrollment window (see [Table 3](#)) unless the repeat testing is necessary to establish a baseline CD4 count, in which case enrollment will occur no sooner than 16 days after the date that blood was drawn for the baseline CD4 count.

If clinical assessment on Day 0 suggests significant changes may have occurred since the screening visit, then the physical examination, complete blood count, prothrombin / international normalized ratio of partial thromboplastin time, blood chemistries and urinalysis done at screening must be repeated, as appropriate, and results received before the participant receives the study injections. Pregnancy test results for female participants must be obtained prior to the study injections.

After Day 0, deviations from the visit windows in completing study visits are discouraged and will be recorded as protocol deviations, but are permitted, at the discretion of the PI (or designee), in consultation with the sponsor, in the interest of obtaining participant safety and immunogenicity evaluations following study injections.

Study visit procedures and tests through Day 336 include the following as indicated in the SOE ([Table 3](#)):

- Clinical evaluations: targeted physical examination and vital signs (both pre- and at about 30 minutes post-vaccination on Day 0)
- Interim medical history, including any new medications taken
- Adverse event documentation
- Study vaccine/placebo injections
- Diary Card: Baseline in the evening on the day of the injections; 7-day diary card for self-assessment by participant
- HIV risk assessment and risk counseling
- HIV testing (including pre/post-test counseling)
- Urine pregnancy testing and counseling
- Urinalysis
- CBC w/ diff
- CD4
- Optional Procedures:
 - Leukapheresis (with safety tests before and after procedure) (Day 14)
 - Sigmoid Biopsy (with GI and dietary questionnaires and safety tests prior to biopsy) (Day 14)
 - Lymph node biopsy (with safety tests prior to biopsy) (Day 14)

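### Section 9.1.5 joins the platelet and hemoglobin limits for leukapheresis with *or*; as a gate on a later count this lets a participant with one low value proceed (minor, probably a slip for *and*)

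*Protocol*

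**What the plan says.** Protocol Section 9.1.5 sets the blood-count condition for leukapheresis in one sentence: "Leukapheresis will be performed on participants whose platelet counts or hemoglobin counts meet the protocol inclusion criteria". It names no particular test or date. A little further on, the same section warns: "Leukapheresis can occasionally cause nausea and may temporarily lower platelet count".

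The limits it points to are in Section 8.4, item 10. Criterion 10a sets hemoglobin at 11.0 g/dL or more for women and 11.5 g/dL or more for men. Criterion 10c reads "Platelets: 150,000 to 450,000" per mm³. Section 8.4 requires every listed criterion to be met for entry.

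Blood counts are available later. Table 3 schedules a CBC at screening and on Days 0, 1, 7 and 14. Footnote 10 to that table adds: "For the leukapheresis procedure, up to 10mL of blood will be drawn for safety tests within 2 days before and after the procedure". It does not list which tests these are. The SAP does not address the point.

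**The concern.** Leukapheresis here is an optional research procedure in healthy volunteers who, by Section 5.6.3, gain no direct benefit. A blood-count condition for such a procedure should exclude anyone with a relevant low count. Joined by *or*, the condition is met when either count is acceptable, so a low platelet count is excused by a normal hemoglobin and the reverse.

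The platelet side matters more, because the section itself warns of a further fall. Precise wording also has practical value. Clinical visits take place at two Bangkok sites, while leukapheresis is done at other institutions (Sections 5.10 and 9.1.5), so staff applying the rule may not be those who know what was meant.

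**Working it through.** No sample size, power or error rate is involved, and the plan gives no figure to reproduce. The check is a reading of the text plus some small sums.

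**1. Which count does the sentence act on?** Section 8.4 makes 10a and 10c compulsory, so every correctly enrolled participant passed both at screening. Applied to screening, the sentence would exclude nobody under either connector. It has a function only on a later count. This is an inference from redundancy, not something the text states.

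**2. What does the connector do on that later count?**

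| Platelets | Hemoglobin | Qualifies with *or* | Qualifies with *and* |
|---|---|---|---|
| within limits | within limits | yes | yes |
| out | within limits | yes | no |
| within limits | out | yes | no |
| out | out | no | no |

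As written, 3 of 4 combinations qualify; with *and*, 1 of 4.

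**3. Which later results exist?** Visit 4 falls on Days 12 to 17 (Day 14, −2/+3).
- Screening CBC (Day −45 to −16): 12 + 16 = 28 to 17 + 45 = 62 days earlier.
- Day 7 CBC (Days 5 to 9): 12 − 9 = 3 to 17 − 5 = 12 days earlier.
- Day 14 CBC: same visit, with no stated order relative to the procedure.
- Footnote 10 draw: within 2 days before the procedure.

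These intervals show only that several results could be meant. They do not measure risk.

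**4. Are both halves equally important?** For hemoglobin, compare blood removed at Visit 4. Under footnote 4, leukapheresis participants skip the draws for B-cell analysis, flow cytometry, innate cells, transcriptomics and additional testing: 30 + 20 + 20 + 20 + 30 = 120 mL. Instead they give 8.5 mL for storage, up to 20 mL for safety tests, and lose about 10 mL of red cells: 8.5 + 20 + 10 = 38.5 mL at most. The 10 mL is red cells and the rest whole blood. To reverse the comparison, its whole-blood equivalent would have to exceed 120 − 28.5 = 91.5 mL, that is, a hematocrit below 10/91.5, or about 11%. About 150 mL of plasma is also removed, but that is not red cells. The hemoglobin half is therefore a slight concern, and low platelets are the main one.

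**5. Does another visible rule require both counts?**
- The serial CBCs and the footnote 10 draw supply results but no decision rule. Section 9.1.5 does not point to footnote 10.
- Section 8.3 says that abnormalities that would "increase the risk to a participant will preclude their participation in optional procedures". The clause sits in text on mucosal collections and sigmoid biopsies and sets no count limit. It recurs in footnote 7 of Table 3, but the leukapheresis row carries footnote 4.
- Exclusion 2 in Section 8.5 covers a diagnosed "platelet disorder requiring special precautions", not a low count first found at Visit 4.
- Section 8.6.1 lets the investigator withdraw someone whose "health or safety may be compromised by further participation". This is discretionary.

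None of these replaces the *or* or says which result decides.

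**The case against.** The strongest reply is that the sentence mentions no pre-procedure test. It refers to the inclusion criteria, and item 10 there is a screening list. On that reading it restates limits everyone has already met, and the connector changes nothing. It is true that the text does not say this. A reader might infer that the protocol expressly permits leukapheresis after a failed pre-procedure count; the documents do not support that. What stands is narrower. The only reading on which the sentence does anything is as a later gate, and there it is too loose.

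The second reply is that the preclusion clause in Section 8.3 is mandatory and speaks of optional procedures generally, which include leukapheresis. If a low count raises risk, the clause bars the procedure. This carries weight as a backstop and is one reason harm is unlikely. It still leaves the numeric condition to judgment when Section 9.1.5 sets out to state one.

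Third, the red-cell comparison shows that a low-hemoglobin participant loses less at this visit than under the routine draws, for which the visible text sets no hemoglobin gate. That is accepted, and low hemoglobin should not be presented as an equal hazard.

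Finally, the Clinical MOP and the Appendix D consent forms are not in the available text and may state the rule correctly. That would lower the practical risk further but would not correct the protocol sentence.

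**Conclusion.** The point holds as a minor participant-safety wording error. Section 9.1.5, used as a gate on a later count, allows a participant with one low value, chiefly low platelets, to proceed, and no visible text requires both counts to be in range. It is most likely a drafting slip for *and*.

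The size is 3 qualifying combinations out of 4 instead of 1. How many participants that represents cannot be estimated, because neither the number undergoing leukapheresis nor the distribution of Day 14 counts is given.

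The conclusion rests on two assumptions: that the sentence is meant to act after enrollment, and that no unseen procedure document overrides it.

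Three stronger readings are not supported:
- That Section 9.1.5 contradicts Section 8.4. It does not, because Section 8.4 governs enrollment.
- That participants are likely to be harmed. The repeated CBCs, the safety tests, the preclusion clause and investigator discretion argue against it.
- That the trial's results are affected. The primary safety and IgG analyses do not depend on this sentence.

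**What to change.** At the next amendment, replace the sentence with:

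> Leukapheresis will be performed only on participants whose platelet count and hemoglobin both meet inclusion criteria 10a and 10c on a CBC drawn within 2 days before the procedure.

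Then make sure that result will exist. Either state in footnote 10 that the pre-procedure safety tests include a CBC, or require the Visit 4 CBC to be drawn and resulted before the procedure starts. The first option is needed because footnote 10 lists no analytes. Table 3 allots 2 mL to the CBC and CD4 draw, which fits within the 10 mL allowance.

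The cost is one sentence and a footnote edit. A few volunteers may be deferred from an optional procedure. Because 10c has an upper limit, the wording would also defer anyone with platelets above 450,000, which is not the harm at issue. If that is unwanted, apply only the lower limit of 150,000.
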